2.1.3 Secondary Objectives and Endpoints

Secondary	
Objective	Endpoint
To assess the effect of setanaxib on urine protein to creatinine ratio (UPCR) compared to placebo.	
 The ratio of UPCR at 24 weeks compared to baseline; and Percentage of patients with a 25% reduction in UPCR at 24 weeks, compared to baseline.
To assess the effect of setanaxib on estimated glomerular filtration rate (eGFR) compared to placebo.	The ratio of eGFR at 24 weeks compared to baseline.
To assess the plasma exposure of setanaxib and its active metabolite GKT138184.	
Pre-dose and post-dose plasma concentrations of setanaxib and GKT138184 at a steady state. The following PK properties will be calculated:
 
 Area under the concentration-time curve over 24 hours at steady state ($AUC_{0-24-ss}$); Minimum plasma concentration at steady state (C_{min-ss}); and Maximum plasma concentration at steady state (C_{max-ss}).

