3.5.1 Urine Protein to Creatinine Ratio (UPCR)

The ratio of UPCR at 24 weeks compared to baseline will be analyzed using a mixed model repeated measurement (MMRM) approach and incorporate UPCR data from 6 weeks, 12 weeks and 24 weeks. Baseline and 24 weeks UPCR will be calculated as the geometric mean of 2 assessments and log-transformed prior to inclusion in the analysis model. The model will include fixed effects for treatment, visit, and treatment by visit interaction, along with the log-transformed baseline value as a covariate. Patient will be included as a random effect. An unstructured covariance matrix will be used to model the within patient correlation of data. If the model does not converge, other covariance structures may be considered. The Kenward-Roger approximation to estimate the degrees of freedom will be used. Model assumptions will be assessed using residual plots (such as q-q plots, histograms) and, if not met, other data transformations or non-parametric approaches may be considered. The LS mean and 2-sided 95% confidence intervals will be estimated.

The analysis will be implemented using SAS® Proc Mixed. Sample SAS code below:

```
*****
** TRT          = treatment group
** VISIT        = Visit name
** USUBJID      = Patient ID
** CHG_UPCR     = Change of log-UPCR at each visit from baseline
** BASE        = log-baseline UPCR
```

```
*****  
proc mixed data=data;  
  class TRT USUBJID VISIT;  
  model CHG_UPCR = TRT VISIT BASE TRT*VISIT/ddfm=kr;  
  repeated VISIT/ sub = USUBJID type = un;  
  estimate 'Week 24 effect' TRT -1 1;  
  lsmeans TRT*VISIT/cl pdiff;  
run;
```

The proportions of patients achieving a 25% reduction in UPCR at 24 weeks from baseline in the setanaxib group will be compared to placebo group using a Fischer's exact test.

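### The UPCR contrast labelled as the Week 24 effect omits the treatment-by-visit coefficients, so it returns the average over Weeks 6, 12 and 24

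*SAP*

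**What the plan says.** SAP 2.1.3 lists the first UPCR endpoint as "The ratio of UPCR at 24 weeks compared to baseline; and". SAP 3.5.1 analyses it with an MMRM that is to "incorporate UPCR data from 6 weeks, 12 weeks and 24 weeks". On the model terms the text says: "The model will include fixed effects for treatment, visit, and treatment by visit interaction, along with the log-transformed baseline value as a covariate". It asks for LS means with two-sided 95% confidence intervals.

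The sample PROC MIXED code agrees with the text on fixed effects: "model CHG_UPCR = TRT VISIT BASE TRT*VISIT/ddfm=kr". Two later statements in the same call bear on the Week 24 result:

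- the ESTIMATE statement, "estimate 'Week 24 effect' TRT -1 1";
- the LSMEANS statement, "lsmeans TRT*VISIT/cl pdiff".

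The code comments define the visit variable as "VISIT = Visit name" and TRT only as the treatment group. The text does not say which of the two outputs supplies the reported Week 24 result.

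The text also states "Patient will be included as a random effect" and asks for an unstructured within-patient covariance matrix. The code has a REPEATED statement with an unstructured matrix and no RANDOM statement.

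**The concern.** In a model with a treatment-by-visit interaction, the treatment effect at one visit is identified only through the interaction terms. The contrast labelled Week 24 has none. VISIT main-effect coefficients are not what is missing, because they cancel in a treatment difference; the TRT*VISIT coefficients are.

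The label invites a programmer to report this line. Protocol 1.5 describes reduction in proteinuria as the preliminary efficacy endpoint, and Protocol 3.1 says the study is meant to guide later Phase 2/3 designs. No formal testing is planned, so the estimate and its interval are the efficacy information. Reporting a three-visit average as the Week 24 effect would understate an effect that builds over time and overstate one that fades.

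The line could also be reused. SAP 3.5.2 applies a similar MMRM to eGFR, as a fallback if the imputation-based analysis fails and otherwise as a sensitivity analysis. If all the post-baseline eGFR visits named in the imputation code (Weeks 2, 6, 12, 18 and 24) entered that model, Week 24 would carry one fifth of the weight.

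**Working it through.** The plan gives no effect size, SD or power for UPCR, so there is no planned figure to reproduce. The check is algebraic, with assumed profiles to show size.

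**Inputs from the documents.** Two treatments, three visits (6, 12, 24), fixed effects TRT, VISIT, BASE and TRT*VISIT (SAP 3.5.1). Allocation is 2:1 with about 18 patients (SAP 2.2.1), hence 12 versus 6.

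**Step 1: what the contrast estimates.** Let d6, d12 and d24 be the setanaxib-minus-placebo differences in log-UPCR change. With the design matrix in PROC MIXED's over-parameterised form (intercept, 2 TRT, 3 VISIT, BASE, 6 TRT*VISIT columns), a contrast L is estimable if L(X'X)⁻(X'X) = L.

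- `TRT -1 1` with all interaction coefficients zero: not estimable.
- `TRT -1 1` with interaction coefficients -1/3 (three times) and +1/3 (three times), the equal filling PROC MIXED applies: estimable, and equal to (d6 + d12 + d24)/3.
- `TRT -1 1 TRT*VISIT 0 0 -1 0 0 1`, visits ordered 6, 12, 24: estimable, and equal to d24.

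Neither reading of the line as written gives d24.

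**Step 2: size on the ratio scale.** The printed value is exp[(d6 + d12 + d24)/3], the geometric mean of the three visit ratios. For example, (0.95 × 0.88 × 0.75)^(1/3) = 0.627^(1/3) = 0.856. All profiles below are assumptions.

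| Assumed ratio at Weeks 6 / 12 / 24 | Line prints | Week 24 ratio |
|---|---|---|
| 0.95 / 0.88 / 0.75 | 0.856 | 0.75 |
| 1.00 / 1.00 / 0.75 | 0.909 | 0.75 |
| 0.75 / 0.75 / 0.75 | 0.750 | 0.75 |
| 0.70 / 0.80 / 0.95 | 0.810 | 0.95 |

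In the first row a 25% reduction is printed as 14%. In the last row a 5% reduction is printed as 19%.

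**Step 3: precision.** Assume complete data, equal variances and a common within-patient correlation ρ. Then SE(average)/SE(Week 24) = √[(1 + 2ρ)/3], whatever the SD: 0.775 at ρ = 0.4, 0.856 at ρ = 0.6 and 0.931 at ρ = 0.8. The printed SE would be 7% to 23% smaller than the Week 24 SE.

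**Step 4: scale against sampling error.** Without covariate adjustment the Week 24 SE is SD × √(1/6 + 1/12) = 0.5 × SD. For assumed log-scale SDs of 0.7 and 0.3 this is 0.35 and 0.15. The first row's gap, ln(0.856/0.75) = 0.13, is about 0.4 to 0.9 SE. The last row's gap, ln(0.95/0.810) = 0.16, is about 0.5 to 1.1 SE.

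**Step 5: the other output.** LSMEANS on six TRT*VISIT cells gives 6 × 5/2 = 15 pairwise differences. One of them is setanaxib versus placebo at Week 24, which is the quantity the endpoint needs.

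**The case against.** A reader might infer that the trial's main efficacy estimate is for the wrong quantity. The documents do not support that. The text names Week 24 as the target and asks for LS means with 95% confidence intervals. The LSMEANS statement carries the option for confidence limits and the ESTIMATE statement does not, so the output that best matches the text is the correct one. Nothing says the ESTIMATE line is what will be reported. The code is offered as a sample, and SAP 7 places detailed programming specifications in a separate document. UPCR is a secondary endpoint, and the protocol treats any modelling and p-values as nominal. All this stands, and it lowers the severity. It does not make the labelled line correct or settle which output prevails.

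A reader might also infer that the true effect will be understated. The direction depends on the time course, which the documents do not give, and Step 2 shows it going either way.

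Finally, a reader might take the random-effect sentence to mean that the fitted model is unidentifiable. The code does not fit that effect; it specifies a coherent unstructured MMRM. A patient variance is redundant on top of an unstructured matrix, but it could have a role under a simpler structure, which the SAP allows if the model does not converge. This is a minor mismatch between text and code, separate from the contrast.

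**Conclusion.** The point holds. As written, the line labelled Week 24 returns the unweighted mean of the Week 6, 12 and 24 treatment differences, and it gives the Week 24 effect only when that mean happens to coincide with it. This follows from the stated model and needs no assumption about data. The sizes (0.856 against 0.75, and 0.810 against 0.95) and the 7% to 23% understatement of the SE rest on assumed effect profiles, correlations and complete data.

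The consequence is a risk of misreporting a secondary result, since the same call already produces the correct Week 24 difference and the SAP leaves open which is used. It should be corrected before database lock. It does not show that the planned efficacy analysis as a whole is invalid.

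**What to change.** Preferred: delete the ESTIMATE line and state in SAP 3.5.1 that the reported result is the Week 24 setanaxib-minus-placebo LS-mean difference from TRT*VISIT, with its 95% confidence interval, both exponentiated to a ratio. This avoids any dependence on the order of factor levels.

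Alternative: keep a contrast and write it as `TRT -1 1 TRT*VISIT 0 0 -1 0 0 1 / cl`. VISIT must then be coded 6, 12, 24, because visit names sorted as text run Week 12, Week 24, Week 6 and would put Week 6 in the last position. TRT must be coded so that placebo sorts first, or the sign reverses.

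Apply the same rule to the eGFR MMRM in SAP 3.5.2. As a separate minor edit, reconcile the patient random-effect sentence with the code, either by removing it or by limiting it to a named fallback covariance structure.

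The cost is one line of code and a few sentences of SAP text, with no change to data collection or to the model.

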3.5.2 Estimated Glomerular Filtration Rate

The eGFR data will be log-transformed prior to analysis. Data included at baseline and at 24-weeks will be the log of the geometric mean of 2 assessments, collected at least 1 week apart. eGFR data are such that it is possible there will be a small number of patients with extreme outlying data. Therefore, the analysis of the ratio of eGFR at 24 weeks compared to baseline will be based on a Robust Regression approach. In order to handle missing data, the analysis will be performed over 3 phases: an imputation, analysis, and pooling phase, as described below.

Imputation phase

During the imputation phase, missing data for eGFR will be imputed 25 times to generate 25 datasets. Multiple imputation will be performed in as follows:

- If missing data follows non-monotone pattern:
 - (a) First, non-monotone missing values will be imputed to create a monotone missing pattern.
 - (b) Then, the remaining monotone missing values will be imputed using a regression method sequentially imputing data across successive visits.
- If missing data follows monotone pattern:
 - (c) Monotone missing values will be imputed using a regression method sequentially imputing data across successive visits.

Sample SAS code below:

```
*****  
** TRT = treatment group  
** VAL2, VAL6, VAL12, VAL18, VAL24a, VAL24b = eGFR value at 2, 6, 12, 18  
                                         and 24 weeks, respectively  
** SCR1 = Screening Visit 1 eGFR value  
** SCR2 = Screening Visit 2 eGFR value  
*****  
  
  (a) proc mi data=data nimpute=25 seed=483794 out=mono;  
        mcmc chain=single impute=monotone;  
        by TRT;  
        var SCR1 SCR2 VAL2 VAL6 VAL12 VAL18 VAL24a VAL24b;  
run;
```

```
(b)      proc mi data=mono nimpute=1 SEED=2019301 OUT=imputed;
          class TRT;
          var SCR1 SCR2 VAL2 VAL6 VAL12 VAL18  VAL24a VAL24b;
          monotone regression;
          by _imputation_;
          run;

(c)      proc mi data=data nimpute=25 SEED=2019301 OUT=imputed;
          by TRT;
          monotone regression;
          var SCR1 SCR2 VAL2 VAL6 VAL12 VAL18 VAL24a VAL24b;
          run;
```

Analysis phase

In the analysis phase, the ratio of eGFR at 24 weeks compared to baseline will be calculated for each patient within each imputed dataset. The ratio of eGFR of the log-transformed data will be analysed using Robust Regression with independent variables of treatment and log-transformed baseline eGFR. M-estimation will be used with Huber weights. Sample SAS code below:

```
*****
** TRT = treatment group
** CHG = Change of log-eGFR baseline ratio at 24 weeks
** BASE = log-baseline eGFR
*****

proc robustreg data=chg method=m (wf=huber) outest=chg1 covout;
  by _imputation_;
  class TRT;
  model CHG = BASE TRT;
run;
```

Pooling phase

In the pooling phase, the results from these 25 analyses will be combined using Rubin's method to construct the treatment estimate using the parameter estimates and associated standard errors. Sample SAS code below:

```
proc mianalyze data=chg1;
  modeleffects estimate;
  stderr stderr;
  ods output ParameterEstimates=est2;
run;
```

If the multiple imputation approach is such that the model convergence is questionable and the given parameter estimates cannot be obtained, then the ratio of eGFR at 24 weeks compared to baseline will be evaluated using similar MMRM model as for UPCR, otherwise, MMRM analysis will be considered as sensitivity analysis.

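### SAP 3.5.2 contradicts itself on the eGFR imputation scale: the text puts the log transformation first, but the sample code imputes plain eGFR values for a log-ratio analysis

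*SAP*

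**What the plan says.** The text of SAP 3.5.2 opens with "The eGFR data will be log-transformed prior to analysis". It then says that "the analysis will be performed over 3 phases: an imputation, analysis, and pooling phase, as described below", which makes imputation part of the analysis. Baseline and Week 24 enter as the log of the geometric mean of two assessments.

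The sample code says something else. In the imputation phase, "missing data for eGFR will be imputed 25 times to generate 25 datasets", and the legend describes the inputs as "SCR1 = Screening Visit 1 eGFR value" (likewise for Screening Visit 2) and "VAL2, VAL6, VAL12, VAL18, VAL24a, VAL24b = eGFR value at 2, 6, 12, 18" and 24 weeks. These are eight variables, none labelled as a log. Step (a) is specified by "mcmc chain=single impute=monotone"; steps (b) and (c) use monotone regression. None of the three calls has a TRANSFORM statement or a minimum.

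In the analysis phase, after imputation, "the ratio of eGFR at 24 weeks compared to baseline will be calculated for each patient within each imputed dataset". Only here does the code legend mention logs: "BASE = log-baseline eGFR", and a change in log-eGFR as the response of the robust regression.

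**The concern.** A programmer who follows the sample code would impute on the mL/min scale and take logs afterwards. Both imputation methods are normal models with a single residual SD per variable. The regression that follows treats the log ratio as having a common error, that is, error roughly proportional to eGFR. The two models do not fit together:

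- A common SD in mL/min becomes a large log error for a patient near the entry floor of 30 and a small one for a patient near 100.
- A normal draw can be zero or negative. Its log is undefined, so the response is missing, the patient leaves that imputed data set, and the 25 fits are pooled over differing numbers of patients without any warning.

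This is the main analysis of the eGFR secondary endpoint. Protocol 1.5 also relies on eGFR to check that the drug does not harm the kidney, so patients with low eGFR matter for its interpretation.

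**Working it through.** **1. Inputs from the documents.** About 18 patients at 2:1, so 18 × 2/3 = 12 and 18 × 1/3 = 6; entry eGFR at least 30; eight imputation variables; 25 imputations. The documents give no eGFR SD and no missing-data rate, so there is no plan figure to reproduce. Everything on variability and dropout below is assumed.

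**2. Is proportional error plausible?** Protocol Appendix B gives eGFR as creatinine to the power −1.209 above the CKD-EPI knot and −1 for bedside Schwartz. Proportional creatinine error therefore gives proportional eGFR error. For a man, the knot lies at 141 × 0.993^age: 141 × 0.993^50 ≈ 99 at age 50 and 141 × 0.993^18 ≈ 124 at age 18. Below such values the −1.209 exponent applies. This makes proportional error plausible over most of the range; it does not prove it.

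**3. Noise for one imputed value.** If s is the residual SD in mL/min and μ the patient's level, the log-scale SD is about s/μ. Simulation: one patient lacks the final value; the coefficients and residual variance of a normal regression are drawn from their posterior; 25 draws; 2,000 repetitions; other patients' baseline log-uniform on 30–120. With 16 complete patients, 2 predictors and CV 8%, raw-scale imputation gives relative SDs of 0.2175, 0.1055 and 0.0712 at eGFR 30, 60 and 100. In mL/min these are 0.2175 × 30 = 6.5, 0.1055 × 60 = 6.3 and 0.0712 × 100 = 7.1: nearly one SD for all. Log-scale imputation gives 0.105, 0.095 and 0.102.

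Ratio of raw-scale to log-scale noise, shown as CV 8% / CV 15% / constant SD of 6 mL/min:

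| Complete patients, predictors | eGFR 30 | eGFR 60 | eGFR 100 |
|---|---|---|---|
| 16, 2 | 2.08 / 2.06 / 1.64 | 1.11 / 1.10 / 0.90 | 0.70 / 0.69 / 0.55 |
| 16, 6 | 1.74 / 1.78 / 1.41 | 1.02 / 1.04 / 0.97 | 0.73 / 0.76 / 0.65 |
| 11, 2 | 1.96 / 1.95 / 1.63 | 1.06 / 1.06 / 0.92 | 0.70 / 0.69 / 0.58 |
| 5, 2 | 1.71 / 1.61 / 1.58 | 0.98 / 1.03 / 0.99 | 0.71 / 0.69 / 0.65 |

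Under proportional error the ratio is 1.6–2.1 at eGFR 30 and 0.69–0.76 at eGFR 100. Over all settings, the eGFR 100 range is 0.55–0.76.

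**4. Non-positive draws, one patient.** With known parameters, P(draw ≤ 0) = Φ(−μ/s). For s = 6 and μ = 30 this is Φ(−5) = 3 × 10⁻⁷; for s = 10 it is Φ(−3) = 0.001. Parameter uncertainty at this sample size raises it. For a patient at eGFR 30 with 2 predictors, per draw (at least one in 25):

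| Complete patients | CV 8% | CV 15% |
|---|---|---|
| 16 | 0.2% (4%) | 2.3% (35%) |
| 11 | 0.4% (9%) | 3.4% (42%) |
| 5 | 4.8% (50%) | 9.9% (69%) |

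At eGFR 60 or above with 11 or 16 complete patients and 2 predictors, it is at most about 0.3% per draw.

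**5. Whole trials.** 18 patients, true eGFR log-uniform 30–130, visit CV 5/7/10% paired with 24-week drift SD 8/10/15%, regression pooled over arms as in step (b), 25 imputations. Ranges are over repeated runs.

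| Missingness | Raw/log ratio | Trials with any non-positive draw |
|---|---|---|
| Three patients last seen at Week 6, lower half of eGFR | SD 1.57 to about 1.7 | 15–19%, 41–51%, 80–87% |
| Three patients last seen at Week 6, unrelated to eGFR | RMSE 1.19–1.35 | 7–9%, 27–28%, 57–59% |
| One patient lost after Week 18, unrelated to eGFR | SD 1.02 to about 1.2 | about 0–10% |

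**6. The path the SAP would take.** These dropout patterns are monotone, so SAP 3.5.2 sends them to step (c), which runs by arm. In a placebo arm of 6 with one patient last seen at Week 6, the first regression has 4 predictors plus an intercept, 5 parameters for 5 complete patients, and cannot be estimated on either scale. In a setanaxib arm of 12 with two such dropouts, the last regression has 10 − 8 = 2 residual degrees of freedom. The SD ratio is then 1.31/1.34/1.08, but log-scale SD is itself 0.25–0.45, and non-positive raw draws occur in 74–97% of trials, mainly because of those 2 degrees of freedom.

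**The case against.** The strongest objection is textual. The section puts the log transformation before the analysis and counts imputation as a phase of the analysis, so the narrative can fairly be read as logging first. The contrary evidence is labels in sample code, and SAP section 7 defers detail to programming specifications that are not available here. This stands: a reader might infer that the SAP prescribes imputation of untransformed eGFR, but it never says so. It does not remove the inconsistency, because the same section writes log wherever it labels an analysis variable as one and leaves it off all eight imputation inputs.

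A reader might also infer that the noise is simply inflated. It is inflated at low eGFR, about right at 60 and too small at 100, and only if error is proportional. If the SD were constant in mL/min, the larger log noise at low eGFR would be real.

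A claim that low-eGFR dropouts get materially downward-biased imputations is not supported either. The simulated bias in the imputed log ratio was −0.01 to −0.06, small beside the imputation SD, and it depends on how non-positive draws are handled.

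The severe missingness scenario is a choice. Protocol 4.3 and 5.4 encourage visits after stopping drug, ask for data to Week 24 and allow replacement. An early termination visit helps less, because SAP 3.1.2 assigns it by study day and an early one does not supply Week 24.

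Finally, an MMRM modelled on the log-scale UPCR analysis is planned as the sensitivity analysis, and nothing is formally tested. That limits the consequences. As a replacement, though, the MMRM applies only when convergence is questionable and estimates cannot be obtained; a patient dropping out of a few imputed data sets triggers neither.

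**Conclusion.** The point holds as an inconsistency within SAP 3.5.2 that should be resolved before database lock. Run as printed, the code imputes on the mL/min scale for a log-ratio analysis. With proportional error, this overstates imputation noise near eGFR 30 by about 1.6 to 2.1 times and understates it near eGFR 100 (0.69–0.76 times; 0.55–0.76 over all settings tried). It also permits draws that have no log.

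The practical size is uncertain. It rests on assumed variability and dropout, and the trial-level figures use pooled regression. The effect on the treatment estimate or its interval after Huber M-estimation was not quantified, so no claim is made that the eGFR result would be distorted. If no eGFR value is missing, there is no effect.

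**What to change.** Add one sentence to SAP 3.5.2: the natural log of each individual eGFR value (`SCR1`, `SCR2`, `VAL2`, `VAL6`, `VAL12`, `VAL18`, `VAL24a`, `VAL24b`) is taken before PROC MI, and the logs are imputed. Relabel the sample-code variables accordingly. After imputation compute

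- `BASE` = mean(log `SCR1`, log `SCR2`)
- `CHG` = mean(log `VAL24a`, log `VAL24b`) − `BASE`

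Since log √(ab) = (log a + log b)/2, these are the SAP's log geometric means, so nothing changes for patients with complete data. Every imputed eGFR, once exponentiated, is positive by construction.

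The cost is one sentence and a short data step. No new data are needed, and the change agrees with Protocol 9.2.2, which already calls for log transformation before analysis.

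This does not cure the separate problem of imputing eight variables by arm with about 6 placebo patients, which needs its own correction.

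### The eGFR pooling code does not connect to the regression output, and without a complete-data df its 95% limits would be about 9% to 15% too narrow at 18 patients.

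*SAP*

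**What the plan says.** SAP 3.5.2 sets out three phases for the eGFR ratio at week 24.

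- Imputation: "missing data for eGFR will be imputed 25 times to generate 25 datasets".
- Analysis: within each data set, "Robust Regression with independent variables of treatment and log-transformed baseline eGFR". The sample code is "proc robustreg data=chg method=m (wf=huber) outest=chg1 covout", run by imputation with treatment as a class variable.
- Pooling: the 25 results are "combined using Rubin's method to construct the treatment estimate using the parameter estimates and associated standard errors". The sample code is "proc mianalyze data=chg1", followed by "modeleffects estimate" and "stderr stderr".

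Nothing stands between the analysis and pooling blocks. Neither the code nor the prose gives a complete-data df or a small-sample rule.

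For UPCR, SAP 3.5.1 states: "The Kenward-Roger approximation to estimate the degrees of freedom will be used". The end of SAP 3.5.2 plans an MMRM like the UPCR one for eGFR, as the fallback if the imputation route fails and as a sensitivity analysis otherwise.

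**The concern.** There are two separate defects in one short step.

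First, the blocks do not fit together. The regression step saves one column per model parameter with added covariance rows. The pooling step looks for one effect column and one standard-error column. The printed pair therefore cannot run, and the repair is left to whoever programs it. The obvious repair, routing the parameter-estimates table into `chg1`, supplies the right column names. It also brings several rows per imputation (intercept, baseline slope, treatment levels, scale), so a row selection is needed too.

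Second, the df. Rubin's original df formula assumes a large complete-data sample. Here each completed data set has about 18 patients, 12 against 6, and three coefficients. Without a complete-data df, the limits use almost a normal quantile.

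The stake is the stated precision of the main eGFR comparison. Protocol 1.5 gives eGFR two purposes: evaluating treatment effect and checking that the drug does not harm the kidney. The study is also meant to guide later Phase 2/3 designs. On df handling alone, the main eGFR analysis would look more precise than its own sensitivity analysis. A reader could take that as a property of the data.

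**Working it through.** The documents give no df, standard deviation, effect size or interval width for eGFR, so there is no planned figure to reproduce.

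**Inputs from the documents**
- m = 25 imputations (SAP 3.5.2).
- Model: intercept, treatment, log baseline eGFR, so 3 coefficients (SAP 3.5.2).
- N about 18, allocated 2:1 (SAP 2.2.1); maximum 20 (Protocol 9.2.3).
- Complete-data residual df: 18 − 3 = 15; 20 − 3 = 17.

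**Assumptions**
- λ, the share of variance due to missing data, is not given. Range used: 0 to 0.4, with λ = (1 + 1/m)B/T, where B is the between-imputation variance and T the total variance.
- Two-sided 95% limits for eGFR. The SAP states these only for UPCR; for eGFR they would be the procedure default.
- The layout of the `OUTEST=` data set and the infinite default df are standard SAS behaviour. SAS was not run.

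**Step 1: columns.** Written: parameter-named columns plus covariance rows. Read: `estimate` and `stderr`. The names do not match, and no row is selected.

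**Step 2: degrees of freedom.**
- Without `EDF=`: df = (m − 1)/λ² = 24/λ².
- With `EDF = ν`: ν_obs = [(ν + 1)/(ν + 3)] × ν × (1 − λ), and df = 1/(λ²/24 + 1/ν_obs) (Barnard-Rubin).
- Example, N = 18, λ = 0.4: without, 24/0.16 = 150. With, ν_obs = (16/18) × 15 × 0.6 = 8.0, and df = 1/(1/150 + 1/8) = 7.6.

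**Step 3: width and coverage.** Coverage takes the pooled statistic as t with the Barnard-Rubin df.

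| N | λ | df without EDF | df with EDF | critical values | width ratio | coverage without EDF |
|---|---|---|---|---|---|---|
| 18 | 0 | infinite | 13.3 | 1.960 / 2.155 | 0.910 | 92.88% |
| 18 | 0.1 | 2400 | 11.9 | 1.961 / 2.180 | 0.900 | 92.64% |
| 18 | 0.2 | 600 | 10.5 | 1.964 / 2.214 | 0.887 | 92.34% |
| 18 | 0.4 | 150 | 7.6 | 1.976 / 2.328 | 0.849 | 91.45% |
| 20 | 0 | infinite | 15.3 | 1.960 / 2.128 | 0.921 | 93.15% |
| 20 | 0.4 | 150 | 8.65 | 1.976 / 2.276 | 0.868 | 91.91% |

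The unadjusted limits are 9% to 15% narrower at N = 18 and 8% to 13% narrower at N = 20. Conversely, at N = 18 the corrected interval is wider by 2.155/1.960 = 1.10 to 2.328/1.976 = 1.18.

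**Step 4: simulation** (Huber M-estimation, asymptotic covariance, 12:6 at N = 18).
- Complete data, 2500 runs, N = 18: normal quantile 92.0%, t(15) 94.0% with normal errors; 92.0% and 94.2% with contaminated errors. At N = 20: 91.6% to 92.2% against 93.7% to 94.2%.
- With 25 imputations, 500 runs each, N = 18, and 1, 2 or 4 week-24 values missing: 93.6%, 92.0% and 93.2% without the adjustment; 95.0%, 95.2% and 96.2% with Barnard-Rubin. Mean width ratios were 0.905, 0.900 and 0.888. Monte Carlo error is about √(0.05 × 0.95/500) = 1 point. The imputation model was a single regression on treatment, baseline and one earlier visit, simpler than the SAP's.

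**The case against.** The best defence is that this is labelled sample code and that SAP section 7 defers detailed programming specifications to a separate document. That stands for the column mismatch: it would stop the run, be noticed and be corrected. It does not settle the df, because the prose names only Rubin's method and a programmer following it faithfully would have no small-sample rule to apply.

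A reader might infer that intercept, baseline and treatment rows will be pooled as one quantity. The documents do not support that. The SAP prose asks for the treatment estimate, so such pooling would contradict the plan. It is a hazard of a careless repair, not the planned analysis.

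A reader might also infer that eGFR has no small-sample analysis at all. It has one: the MMRM described at the end of SAP 3.5.2 follows the UPCR model and so carries Kenward-Roger df. The gap is confined to the main analysis.

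A third tempting shortcut is to compare 1.960 with t(15) = 2.131. That gives 1.960/2.131 = 0.920, an interval 8.0% too short, with 93.1% coverage if the standard error were exact. But setting `EDF` to 15 does not give t(15); it gives Barnard-Rubin df of 13.3 or fewer, so the shortcut understates the difference.

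Finally, eGFR is a secondary endpoint, SAP 3.1.6 excludes formal testing, and Protocol 9.2 calls any p-values nominal. This limits the consequence. It does not remove it, because an estimate with its interval is then the main product of the analysis.

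**Conclusion.** The point holds as a specification error that should be fixed. The printed pooling step does not read what the regression step writes and does not isolate the treatment contrast. Repairing the columns alone leaves an effectively infinite complete-data df for a regression with 15 to 17 residual df.

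At N = 18 this makes the default 95% limits about 9% to 15% narrower than Barnard-Rubin limits, with coverage of about 92.9% to 91.5%; at N = 20 they are about 8% to 13% narrower. These figures rest on an assumed missing-information share of 0 to 0.4, on 95% limits being reported, and on standard SAS defaults. The simulated shortfalls with imputation are of similar size, within their Monte Carlo error.

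It would go too far to say that the eGFR result is invalid or that the treatment estimate is biased by this. The df affect only the limits and the nominal p-value. Nor is the df the only small-sample weakness: the robust standard error is itself asymptotic.

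**What to change.** In SAP 3.5.2:

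1. Output the `ParameterEstimates` table by `_imputation_` and keep only the setanaxib-versus-placebo row, so that `estimate` and `stderr` exist and hold one contrast per imputation.
2. Run `MIANALYZE` on that data set with `EDF` equal to patients analysed minus 3 (15 at N = 18, 17 at N = 20), set from the actual count. Say in the prose that Barnard-Rubin df are used.
3. State that two-sided 95% limits will be reported, and back-transform the estimate and limits to a ratio, in line with the back-transformation in Protocol 9.2.2.

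This costs a few lines of code and text and needs no new data. It should be done before database lock and unblinding, so that the repair is not chosen with results in view. The price is an interval about 10% to 18% wider at N = 18. A small shortfall would remain with complete data (about 94% coverage in simulation), because `EDF` does not correct the asymptotic standard error. The SAP could say so in one sentence.
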